### 6.2.2. Study Period

Assessments and events will be classified according to the date/time of occurrence relative to date/time of first dose of study treatment.

Study Phase	Definition
Pre-Treatment	Date/time $\leq$ Study Treatment Start Date/time
On-Treatment	Study Treatment Start Date/time < Date/time $\leq$ Last Dose Date + 70 days
Post-Treatment	Date/time > Study Treatment Stop Date + 70 days

For assessment or event on the first dosing day, whether it is Pre-Treatment or On-Treatment should be based on time if available. If time is not available, the first dosing day (Day 1) is considered Pre-Treatment for ECOG, ECG, vital signs, liver events, lab tests, cardiac scan, and other safety domains, and On-Treatment for adverse events and concomitant medications.

Concomitant Medication and Blood and Blood Supportive Care Product start and end dates will be assigned to study time periods in relation to first dose of study treatment as defined below. The start date references time flag variables and end date reference time flag variables will be added to the concomitant medications and blood and blood supportive products datasets, respectively.

- Start relative to treatment: Assign to 'BEFORE' if start date is prior to study treatment start date or if subject has not taken any study treatment or (start date is missing and end date is before study treatment start date). Else assign to 'DURING' if the start date falls into the on-treatment period as defined above or if subject is ongoing (not all study treatment discontinuation records completed) or start date is missing. Else assign to 'AFTER' if start date is after the on-treatment period.
- End relative to treatment: Assign to 'BEFORE' if end date is prior to study treatment start date or if subject has not taken any study treatment. Else assign to 'DURING' if start date falls into the on-treatment period or if subject is ongoing (not all study treatment discontinuation records completed) or (end date is missing and start relative to treatment not 'AFTER'). Else assign to 'AFTER' if start date is after the on-treatment period or (end date is missing and start relative to treatment='AFTER').

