### 6.2.3. Treatment Emergent Flag for Adverse Events

Flag	Definition
Treatment Emergent	
 
• Study Treatment Start Date ≤ AE Start Date ≤ min(Study Treatment Stop Date + 70 day, Start of anti-cancer therapy)
 
• AE Start Date is missing
 

All AE displays will use the “treatment emergent” definition. One additional AE display by preferred term may be generated for the AEs between the start of anti-cancer therapy and Study Treatment Stop Date + 70 day if a subject starts an anti-cancer therapy before the Study Treatment Stop Date + 70 day.

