**6.2.7. Handling of Partial Dates**

Element	Reporting Detail		
General	
 
• Partial dates will be displayed as captured in participant listing displays.
 
• However, where necessary, display macros may impute dates as temporary variables for sorting data in listings only. In addition, partial dates may be imputed for ‘slotting’ data to study phases or for specific analysis purposes as outlined below.
 
• Imputed partial dates will not be used to derive study day, time to onset or duration (e.g., time to onset or duration of adverse events), or elapsed time variables (e.g., time since diagnosis). In addition, imputed dates are not used for deriving the last contact date in overall survival analysis dataset.
 
		
Adverse Events	
 
• Partial dates for AE recorded in the CRF will be imputed using the following conventions: 
 
 Missing start day	First of the month will be used unless this is before the start date of study treatment; in this case the study	
 
 
 
	Missing start day	First of the month will be used unless this is before the start date of study treatment; in this case the study
Missing start day	First of the month will be used unless this is before the start date of study treatment; in this case the study		

Element	Reporting Detail	
		treatment start date will be used and hence the event is considered on-treatment
	Missing start day and month	No Imputation
	Missing end day	Last day of the month will be used.
	Missing end day and month	No Imputation
	Completely missing start/end date	No imputation
Concomitant Medications/ Medical History	
 
Partial dates for any concomitant medications recorded in the CRF will be imputed using the following convention:
 
	
	Missing start day	A '01' will be used for the day
	Missing start day and month	A '01' will be used for the day and 'Jan' will be used for the month
	Missing end day	A '28/29/30/31' will be used for the day (dependent on the month and year).
	Missing end day and month	A '31' will be used for the day and 'Dec' will be used for the month.
	Completely missing start/end date	No imputation

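### The treatment-emergent flag takes in every AE with a missing start date, even when its recorded end date is before the first dose

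*SAP*

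**What the plan says.** Section 6.2.3 gives two bullets for the treatment-emergent flag. The first is a window: "Study Treatment Start Date ≤ AE Start Date ≤ min(Study Treatment Stop Date + 70 day, Start of anti-cancer therapy"). The second is "AE Start Date is missing", with no condition attached. They can only be alternatives, because no record could satisfy both. The section then sets the reach of the flag: "All AE displays will use the “treatment emergent” definition".

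Section 6.2.7 says which AE starts stay without a usable date. If the start is completely missing, or lacks both day and month, the AE entry is "No Imputation".

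For concomitant medications and blood products, Section 6.2.2 orders the checks differently. The start is classed as BEFORE if, among other conditions, "start date is missing and end date is before study treatment start date". Only after that check does a remaining missing start default to DURING.

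**The concern.** An event that ended before the first dose must have begun before it. Had its start date been recorded, the first bullet of Section 6.2.3 would exclude it. Because the start is blank, the second bullet includes it. The same event therefore gets opposite classifications depending on whether a field was filled in, although the record already contains what is needed to settle the matter.

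What is at stake is the content of the AE tables. An event that cannot have been caused by study drug can appear as treatment-emergent in any of them. No efficacy analysis or formal test is affected.

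**Working it through.** No figure in the SAP is in question, so the check applies the rules as written to test records. The dates are assumed for illustration only: first dose 10 March 2021 and treatment stop 1 September 2021, so the window closes at stop + 70 days, 10 November 2021 (unless new anti-cancer therapy starts earlier).

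| Record | AE flag, 6.2.3 as written | Same dates as a medication, 6.2.2 | AE flag with an end-date clause |
|---|---|---|---|
| Start missing, end 15 Feb 2021 | Treatment-emergent | BEFORE | Not treatment-emergent |
| Start and end both missing | Treatment-emergent | DURING | Treatment-emergent |
| Start 1 Feb 2021, complete | Not treatment-emergent | BEFORE | Not treatment-emergent |

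The first row is the defect. The event ended 23 days before first dose (13 days left in February + 10 in March) and is still flagged. The second row shows that the worst-case rule for an undated AE agrees with the medication rule and is left alone by the clause. The third row shows that a pre-dose event with a recorded start is excluded, as intended.

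I looked for any other text in the SAP that would remove the record in the first row and found none.

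Size per affected participant, using the planned numbers in Section 1.2 (about 214 and 106):

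- Belantamab mafodotin arm: 1/214 = 0.47 percentage points.
- Pom/dex arm: 1/106 = 0.94 percentage points.

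These are ceilings. Under the counting rules in Section 4.5.2, a participant counts once per preferred term and once in the any-event row. If the participant has another qualifying event in the same row, the spurious record adds 0 to that row's incidence. The denominators are planned randomised numbers. The tables will use the Safety set, so the exact fractions will differ slightly.

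**The case against.** The strongest defence is that counting undated AEs as treatment-emergent is an accepted worst-case convention, and that the SAP takes the same line for missing relatedness (Section 4.5.2). That holds for AEs with no informative date. It does not cover an AE whose own end date rules out onset on treatment, because nothing is unknown about the side of first dose on which it falls.

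A second objection is that few such records may exist. The version history says Section 6.2.3 was aligned with AE collection in the protocol, which is not shown, and Section 1 leaves further data-handling conventions to a programming specification. If AEs are collected mainly from first dose, the affected set may be close to empty. This stands as a limit on impact. It does not repair the rule, and the lower bound in the first bullet shows that the SAP itself expects some AEs to start before treatment.

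A reader might go further and infer that a year-only start before the year of first dose is also wrongly flagged. The SAP does not establish that. For AEs, Section 6.2.7 lists "Missing start day and month" in a separate row from a completely missing date, and Section 6.2.3 does not say whether a year-only start counts as missing. Nor does the medication check in Section 6.2.2 cover that case; year-only medication starts are handled by imputation ("A '01' will be used for the day and 'Jan' will be used for the month"). In addition, an event with an early start year and no end date is not known to have ended before study drug. This is a gap to clarify and not a demonstrated error.

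The missing-day rule for AEs in Section 6.2.7, under which "treatment start date will be used and hence the event is considered on-treatment", is a separate matter. Changing it would leave the missing-start bullet as it is.

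**Conclusion.** The point holds for one case: an AE with a missing start date and a recorded end date before the first dose. Section 6.2.3 as written misclassifies it, and Section 6.2.2 already contains the check that would prevent this.

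It is a minor point. The error goes in one direction, towards over-counting, with the ceilings shown above. Those figures should not be read as an estimate of the distortion to expect in the tables, since the number of affected records depends on AE collection rules in the protocol. The conclusion rests on reading the two bullets as alternatives and on the programming specification not adding a condition that the SAP omits.

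**What to change.** Amend the second bullet of Section 6.2.3 to read: "AE Start Date is missing", unless the AE end date is before the date of first dose of study treatment. AEs with neither a start date nor an informative end date stay flagged. An end date on the day of first dose also leaves the AE flagged.

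As a clarification only, state how a year-only AE start is handled: a start year before the year of first dose is not treatment-emergent, and a start year equal to it stays under the worst-case rule. The 1 January imputation used for medications should not be borrowed for this. With the illustrative dates above, it would move an AE with only the year 2021 recorded to before the first dose, although that AE may have started on treatment.

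The cost is one clause and one clarifying sentence in the SAP, and about one line of derivation code. No new data are needed.

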**6.2.4. Study Day and Reference Dates**

Calculated as the number of days from First Dose Date:

- Ref Date = Missing → Study Day = Missing
- Ref Date < First Dose Date → Study Day = Ref Date – First Dose Date
- Ref Date ≥ First Dose Date → Study Day = Ref Date – (First Dose Date) + 1

**6.2.5. Assessment Window**

For data summaries by visit, scheduled visits with nominal visit description as well as the worst-case post baseline will be displayed. Unscheduled visits will not be displayed or slotted into a visit window but will be included in the derivation of worst-case post baseline assessment. All un-scheduled visits will be displayed in the listing.

**6.2.6. Multiple measurements at One Analysis Time Point**

When triplicate ECG assessments are taken, mean of the measurement will be calculated first and summary statistics will be based on the calculated mean. This will apply to both baseline and post baseline assessments.

For lab tests on a study day, if more than one assessment is taken on the same day, the test from a central lab will be taken over the test from a local lab. If multiple assessments are taken from the same type of lab, the worst case will be used.

**6.2.7. Handling of Partial Dates**

Element	Reporting Detail		
General	
 
• Partial dates will be displayed as captured in participant listing displays.
 
• However, where necessary, display macros may impute dates as temporary variables for sorting data in listings only. In addition, partial dates may be imputed for ‘slotting’ data to study phases or for specific analysis purposes as outlined below.
 
• Imputed partial dates will not be used to derive study day, time to onset or duration (e.g., time to onset or duration of adverse events), or elapsed time variables (e.g., time since diagnosis). In addition, imputed dates are not used for deriving the last contact date in overall survival analysis dataset.
 
		
Adverse Events	
 
• Partial dates for AE recorded in the CRF will be imputed using the following conventions: 
 
 Missing start day	First of the month will be used unless this is before the start date of study treatment; in this case the study	
 
 
 
	Missing start day	First of the month will be used unless this is before the start date of study treatment; in this case the study
Missing start day	First of the month will be used unless this is before the start date of study treatment; in this case the study		

Element	Reporting Detail	
		treatment start date will be used and hence the event is considered on-treatment
	Missing start day and month	No Imputation
	Missing end day	Last day of the month will be used.
	Missing end day and month	No Imputation
	Completely missing start/end date	No imputation
Concomitant Medications/ Medical History	
 
Partial dates for any concomitant medications recorded in the CRF will be imputed using the following convention:
 
	
	Missing start day	A '01' will be used for the day
	Missing start day and month	A '01' will be used for the day and 'Jan' will be used for the month
	Missing end day	A '28/29/30/31' will be used for the day (dependent on the month and year).
	Missing end day and month	A '31' will be used for the day and 'Dec' will be used for the month.
	Completely missing start/end date	No imputation
New Anti-Cancer Therapy/Radiotherapy/Surgical Procedures for Efficacy Evaluation (e.g., response rate, time to event)	
Start dates for follow-up anti-cancer therapy, radiotherapy (where applicable), and surgical procedures (where applicable) will be temporarily imputed in order to define event and censoring rules for progression-free survival, response rate, time to progression, duration of response or time to response (i.e. start date for new anticancer therapy). The imputed dates will be stored on the anti-cancer therapy, radiotherapy, or surgical procedure datasets.
 
 
If missing start day, month, and year, then no imputation for completely missing dates
 
If missing start day and month, then no imputation should be done
 
If missing start day, then do the following:                             
 
If partial date falls in the same month as the last dose of study treatment, then assign to earlier of (date of last dose of study treatment+1, last day of month).
 
 
 
	

Element	Reporting Detail
	
 
○ If partial date falls in the same month as the subject’s last assessment and the subject’s last assessment is PD, then assign to earlier of (date of PD+1, last day of month).
 
○ If both rules above apply, then assign to latest of the 2 dates
 
○ Otherwise, impute missing day to the first of the month.
 
● If missing end date, then no imputation should be done.
 

Covariates for efficacy analysis (Date of initial diagnosis/Last recurrence/Last progression)	
 
● If both month and day are missing, first of January will be used If only day is missing, first of the month will be used
 

Death date	
If there are partial death dates, then partial death dates will be imputed in order to define event dates for overall survival. The imputed dates will be stored on the time to event dataset.
 
 
● If missing start day and month, then do the following:                             
 
○ If partial date corresponds to the same year as the last known date of last contact, then assign to last known date of last contact.
 
○ Otherwise, impute missing day and month to the first of January.
 
 
 
● If missing start day, then do the following:                             
 
○ If partial date falls in the same month as the last known date of last contact, then assign to last known date of last contact.
 
○ Otherwise, impute missing day to the first of the month.
 
 
 

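### The missing-day rule for AE start dates has no same-month condition, so an AE whose recorded month precedes the month of first dose is flagged treatment-emergent

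*SAP*

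**What the plan says.** SAP section 6.2.7 (Handling of Partial Dates) allows imputation for a limited purpose: "partial dates may be imputed for ‘slotting’ data to study phases or for specific analysis purposes as outlined below". For an AE with the start day missing, the rule is "First of the month will be used unless this is before the start date of study treatment". Where that exception applies, the "treatment start date will be used and hence the event is considered on-treatment".

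Section 6.2.3 defines the flag as "Study Treatment Start Date ≤ AE Start Date ≤ min(Study Treatment Stop Date + 70 day, Start of anti-cancer therapy"). Equality with the treatment start date therefore counts as treatment-emergent. The same section adds: "All AE displays will use the “treatment emergent” definition".

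Section 6.2.7 also limits how far an imputed date can travel: "Imputed partial dates will not be used to derive study day, time to onset or duration". It states that listings show partial dates as they were captured.

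**The concern.** Moving a partial date to the treatment start date is a sensible cautious choice when the event could have begun on either side of first dose, that is, within the calendar month of first dose. For any previous month there is nothing to resolve, because the recorded month and year already place onset before treatment. The rule makes no distinction between the two cases, so in the second it overrides known data.

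What is at stake is the accuracy of the AE incidence tables. An affected event would count in the any-AE, maximum-grade, SAE and, where the term qualifies, AESI tabulations of section 4.5.2. If its relatedness is missing, that section's worst-case convention would also count it as related to study treatment.

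**Working it through.** The SAP states no figure on this point, so the check applies the rule literally and compares it with the same rule restricted to the month of first dose.

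**Inputs.** The imputation rule is from section 6.2.7 and the treatment-emergent definition from section 6.2.3. The dates are assumed for illustration: first dose 15 March 2021, last dose 1 September 2021, no new anti-cancer therapy. The treatment-emergent window is then 15 March 2021 to 1 September 2021 + 70 days = 10 November 2021.

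**Rule as written.** Let F be the first day of the reported month and T the treatment start date. If F < T, the start date is T; otherwise it is F.

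**Rule with a same-month condition.** If F < T and the reported month and year are those of T, the start date is T; otherwise it is F.

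| Reported AE start | As written | Treatment-emergent? | With same-month condition | Treatment-emergent? |
|---|---|---|---|---|
| Jun 2020 | 15 Mar 2021 | yes | 1 Jun 2020 | no |
| Jan 2021 | 15 Mar 2021 | yes | 1 Jan 2021 | no |
| Feb 2021 | 15 Mar 2021 | yes | 1 Feb 2021 | no |
| Mar 2021 | 15 Mar 2021 | yes | 15 Mar 2021 | yes |
| Apr 2021 | 1 Apr 2021 | yes | 1 Apr 2021 | yes |
| Dec 2021 | 1 Dec 2021 | no | 1 Dec 2021 | no |

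Only the first three rows differ, and in each the recorded month rules out onset on treatment. The general argument is short. For any month before that of T, F < T always holds, so the exception always applies. The imputed date then equals T, and the condition "Study Treatment Start Date ≤ AE Start Date" is met with equality.

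**No check against the end date.** Take an AE recorded as starting and ending in February 2021, both days missing. The end-date row of section 6.2.7 imputes the last day of the month, 28 February 2021, while the start is imputed to 15 March 2021. The imputed start falls after the imputed end.

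**Other rows of the same table.**
- New anti-cancer therapy: the special assignment is conditional, "If partial date falls in the same month as the last dose of study treatment" (a parallel condition covers the month of a last assessment of PD), and otherwise the first of the month is used.
- Death date: with the day missing, the special assignment likewise requires the month to match that of last known contact, and otherwise the first of the month is used.
- Concomitant medication: a missing start day becomes the first of the month, with no move to treatment start. An AE and the drug given for it, both recorded as starting in February 2021, would be separated. Under section 6.2.2 the drug starts before treatment, while the AE is on-treatment.

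The AE row moves the date to a reference date without requiring the month to match, which the first two rows do require.

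**The case against.** The strongest reply concerns reach. An affected record must have been entered as an AE, carry a month and year but no day, and fall in a calendar month before first dose. Whether such records exist depends on when AE collection begins. That is a protocol matter, and the SAP does not state it. If non-serious AEs are collected only from first dose, very little remains. Pre-existing conditions may instead be captured as medical conditions at screening (section 6.1.2). This stands, and it is why no count can be given. The June 2020 and January 2021 rows in the illustration show the logic; the month just before first dose is the more realistic case.

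The damage is also contained. Time to onset and duration do not use the imputed date, and a reader of the listings would see the captured month. This stands too.

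A third reply is that the rule errs towards over-inclusion, in line with the plan's handling of a missing AE start date and of missing relatedness. Those rules resolve missing information, whereas this one overrides information that is present, so the parallel fails for months before that of first dose. The same-month case was probably what was intended, and the separate programming specification may handle it so, but the SAP text does not say so.

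A reader might go further and infer that the safety comparison is biased, or that false events are added in both arms. The SAP supports neither. It does not show that such records occur in either arm, gives no reason why they should fall unequally, and plans descriptive AE summaries by arm in section 4.5.2.

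**Conclusion.** The rule is wrong as written. Any AE with a missing start day and a recorded month before that of first dose is classified as treatment-emergent, although its onset is known to precede treatment. Nothing else in the SAP corrects this. The one escape under section 6.2.3 would be a new anti-cancer therapy recorded as starting before the treatment start date.

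The consequence is limited to the treatment-emergent flag and the incidence counts that rest on it. Onset and duration summaries, listings and efficacy results are not affected. The number of records is probably small but cannot be derived from the SAP. The conclusion rests on a literal reading of section 6.2.7, which is how a programmer would be expected to implement it.

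**What to change.** Replace the missing-start-day rule for AEs in section 6.2.7 with:

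> If the partial start date is in the same month and year as the first dose, and any known AE end date is not before the treatment start date, use the treatment start date; otherwise use the first of the reported month.

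AEs from previous months then stay pre-treatment. AEs in the month of first dose keep the cautious assignment unless they are known to have ended before treatment, and AEs in later months are unchanged. The cost is one clause of SAP text and the matching line in the programming specification. No other analysis is altered.

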**Table 2 Assignments for Primary and Alternative Progression and Censoring Dates for PFS Analysis**

Situation	Date of Event (Progression/Death) or Censoring	Outcome Event (Progression/Death) Or Censored
No (or inadequate) baseline tumor assessments  and the subject has not died (if the subject has died follow the rules for death indicated at the bottom of the table)	Randomization	Censored
No post-baseline assessments and the subject has not died (if the subject has died follow the rules for death indicated at the bottom of the table)	Randomization	Censored
Progression documented at scheduled visits and Progression documented without extended loss-to-follow-up time 	Date of assessment of progression	Event
Progression documented between scheduled visits and Progression documented without extended loss-to-follow-up time 	Date of assessment of progression	Event
	Date of next scheduled response assessment [SA1]	Event [SA1]
No progression (or death)	Date of last 'adequate' assessment of response 	Censored
New anticancer treatment started (prior to documented disease progression or death)  .	Date of last 'adequate' assessment of response  (on or prior to starting anti-cancer therapy)	Censored
	Date of starting new anticancer therapy [SA2]	Event [SA2]
Death without extended loss-to-follow-up time 	Date of death	Event
Death or progression after an extended loss-to-follow-up time 	Date of last 'adequate' assessment of response  prior to PD/death (prior to missed assessments)	Censored
	Date of death or progression [SA2]	Event [SA2]
Death or progression after an extended loss-to-follow-up time  from randomization	Date of randomization	Censored
Treatment discontinuation due to clinical PD before PD or death [SA2]	Date of treatment discontinuation [SA2]	Event [SA2]

[SA1]. Alternative rule 1 for handling of intercurrent events for supplementary estimand of PFS

[SA2]. Alternative rule 2 for handling of intercurrent events for supplementary estimand of PFS

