**Table 3 Response confirmation algorithm based on visit-level response**

#	Response at the First Time Point	Response at Subsequent Disease Assessment 	Confirmed Response at the First Time Point
1	sCR	sCR	sCR
2	sCR	CR	CR
3	CR	sCR/CR	
4	sCR/CR	VGPR	VGPR
5	VGPR	sCR/CR/VGPR	
6	sCR/CR/VGPR	PR	PR
7	PR	sCR/CR/VGPR/PR	
8	sCR/CR/VGPR/PR	MR	MR
9	MR	sCR/CR/VGPR/PR/MR	
10	sCR/CR/VGPR/PR/MR	SD	SD
11	sCR/CR/VGPR/PR/MR	PD (any reason)  OR No subsequent disease assessment: subject died or discontinued study or started new anti-cancer therapy before further adequate disease assessment	SD
12	PD (due to reasons other than imaging, i.e., plasmacytoma or bone lesion)	PD (any reason) including PD after initiation of new anti-cancer therapy  OR No subsequent disease assessment: subject died due to PD before further adequate disease assessment and within 49 days of PD at First Time Point (including death due to PD after initiation of new anti-cancer therapy)	PD
13	PD (due to reasons other than imaging, i.e., plasmacytoma or bone lesion)	sCR/CR/VGPR/PR/MR/SD  OR No subsequent disease assessment: subject died due to reasons other than	NE

#	Response at the First Time Point	Response at Subsequent Disease Assessment 	Confirmed Response at the First Time Point
		
PD before further adequate disease assessment
 
OR
 
No subsequent disease assessment: subject discontinued study before further adequate disease assessment
	
14	sCR/CR/VGPR/PR/MR/PD (due to reasons other than imaging, i.e., plasmacytoma or bone lesion)	No subsequent disease assessment: subject has not died, discontinued from study or (except for PD) started new anti-cancer therapy; but as yet has no further adequate disease assessments	
Unconfirmed sCR/CR/VGPR/PR/MR/PD.
 
Will be categorized as NE for final ORR analysis.

15	SD	
Any
 
OR
 
No subsequent disease assessment
	SD
16	PD due to imaging (plasmacytoma or bone lesion)	
Any
 
OR
 
No subsequent disease assessment
	PD
17	NE or missing	
Any
 
OR
 
No subsequent disease assessment
	NE

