1. Subsequent disease assessment is defined as the next adequate (not missing or NE) disease assessment following the first timepoint before (or on the same date of) start of new anti-cancer therapy except for confirmation of PD, for which PD or death due to PD after new anti-cancer therapy are considered for confirmation of PD. No minimal time interval is required for the subsequent disease assessment, but a different sample is required for confirmation.
2. SD does not need to be confirmed.
3. PD due to imaging (i.e., plasmacytoma or bone lesion) does not need to be confirmed.
4. Where criteria are not mutually exclusive, take the first that applies.

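### The day-missing rule for new anti-cancer therapy is tied to the last assessment, not the first PD, so in a narrow sequence of dates it can censor a real PFS event

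*SAP*

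**What the plan says.** Section 6.2.7 states that start dates of new anti-cancer therapy "will be temporarily imputed in order to define event and censoring rules for progression-free survival" and for the other response and progression endpoints. When only the start day is missing, there are three rules:

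- **Last-dose rule.** "If partial date falls in the same month as the last dose of study treatment", the date is the day after the last dose or the month end, whichever comes first.
- **PD rule.** "If partial date falls in the same month as the subject’s last assessment and the subject’s last assessment is PD", the date is the day after PD or the month end, whichever comes first; the clause reads "last assessment is PD, then assign to earlier of (date of PD+1, last day of month". If both rules apply, the later date is used.
- **Default.** "Otherwise, impute missing day to the first of the month".

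Table 2 uses the therapy date. Under the primary rules, the row "New anticancer treatment started (prior to documented disease progression or death)" leads to censoring at the last adequate assessment on or before the therapy start. Footnote 3 of Table 2 lets PD take precedence when both fall on the same day. Table 4 repeats the row and the footnote for TTP, and section 4.3.2.1 makes DoR censoring follow PFS.

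In Table 3, PD not based on imaging needs a further PD or a death due to PD. Row 12 accepts "PD (any reason) including PD after initiation of new anti-cancer therapy", and footnote 1 repeats that "PD or death due to PD after new anti-cancer therapy are considered for confirmation of PD".

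**The concern.** Sections 1.1.1 and 4.2.1 date PFS from the earliest documented PD. The PD rule in section 6.2.7 instead looks at the last assessment. The two are the same visit only if nothing is assessed after the first PD. Table 3 expects a later confirming assessment for non-imaging PD and accepts one made after new therapy has started. That later visit can move the last assessment into the next calendar month and switch the protection off, although it confirms the very progression the rule is meant to protect.

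At stake is the status of individual participants on the primary endpoint. A confirmed progression would be replaced by an earlier censoring date because of an imputed day. Such censoring is informative, because it arises from having progressed and moved on to other therapy. Two participants with identical PD and therapy data could be classified differently only because of where a month ends.

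**Working it through.** **The plan's own figure.** Section 5.2 gives 151 PFS events for 90% power at HR 0.57, one-sided alpha 0.025 and 2:1 allocation.

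- Schoenfeld events: (1.960 + 1.282)² / [(2/9) × (ln 0.57)²] ≈ 150.
- Power with 151 events: 0.903.
- Critical HR: exp(−1.960 / √(151 × 2/9)) = 0.713.

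These agree with the SAP. Nothing below changes them.

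**Applying the rules as written.** Inputs are the three imputation rules and the later-date rule (section 6.2.7), and the censoring row with its same-day footnote (Table 2). A 21-day gap from first to later PD is assumed, from the 3-weekly assessments in sections 1.2 and 6.2.9. The participant is an event if the first PD is on or before the imputed therapy start, and is censored otherwise. The dates are illustrative.

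| Case | Last dose | First PD | Therapy month | Later PD | Imputed, as written | Status | Imputed, first-PD rule | Status |
|---|---|---|---|---|---|---|---|---|
| 1 | 24 Feb | 17 Mar | Mar | 7 Apr | 1 Mar | censored | 18 Mar | event |
| 2 | 3 Mar | 24 Mar | Mar | 14 Apr | 4 Mar | censored | 25 Mar | event |
| 3 | 17 Mar | 17 Mar | Mar | 7 Apr | 18 Mar | event | 18 Mar | event |
| 4 | 10 Feb | 3 Mar | Mar | 24 Mar | 25 Mar | event | 4 Mar | event |
| 5 | 24 Feb | 17 Mar | Apr | 7 Apr | 8 Apr | event | 1 Apr | event |

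In case 1 neither special rule applies, so the default puts therapy 16 days before PD. In case 2 the last-dose rule applies and still gives a date before PD. Cases 3 to 5 show what keeps the event: a last dose on the PD day, confirmation in the PD month, or therapy in the month of confirmation.

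The same-day footnote adds two exceptions. A last dose exactly one day before PD, in the same month, gives an imputed date equal to PD. So does a PD on the 1st of the month under the default. Both stay events.

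**How often the calendar allows it.** I took PD on every day of two years, true therapy start 1 to 20 days after PD, the later PD at 21 days, and the start day always missing. Therapy then falls in the PD month with confirmation in the next month in 34.5% of combinations.

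| Last dose | Censored among those 34.5%, as written | Censored, first-PD rule |
|---|---|---|
| On the PD day | 0% | 0% |
| 21 days before PD | 100% | 0% |
| 42 days before PD | 100% | 0% |

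The 34.5% is a property of the calendar and of these assumptions. It does not estimate how many trial participants are affected.

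**The case against.** The strongest reply is that the clause can be read benignly. Table 3 assigns the confirmed response to the first time point, and section 4.3.2.1 ignores assessments after confirmed progression or new therapy. If the last assessment means the first, later-confirmed PD visit, the problem vanishes. Section 1 also leaves further data-handling detail to the Output and Programming Specification. But section 6.2.7 does not state that meaning, the limit in section 4.3.2.1 is given for ORR and CBR, and one of its end points is the very therapy date being imputed. If the benign reading is intended, the text still needs to say so.

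The second reply is that the path is narrow, and this stands. Section 1.2 ends disease evaluation at confirmed PD or new therapy for participants who stopped treatment for reasons other than PD, and follows participants for survival after PD. Assessment after new therapy is something Table 3 accepts, not the planned routine.

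Three stronger readings are tempting, and the document supports none of them:

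- **Any PD confirmed in the next month is at risk.** With confirmation 21 days later, 69% of PD dates would have it in a later month, but that ignores when therapy began. In the order PD, confirmation, therapy, with no later assessment, the rule works.
- **A later assessment that is not PD does the same harm.** For non-imaging PD, row 13 of Table 3 makes PD followed by stable disease or better not evaluable, so there is no confirmed event to lose. This matters only for imaging PD or PD already confirmed.
- **The treatment comparison is biased between arms.** The same rule applies to both, and the SAP gives nothing from which a direction or size could be derived.

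It is also fair that the final PFS analysis is triggered by counted events, so a lost event partly delays the trigger rather than reducing the total. Supplementary estimand 2 would still count the participant as an event, but at the imputed therapy date.

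**Conclusion.** The point holds as a defect in the stated rule. Read literally, section 6.2.7 with Table 2 turns a real PFS event into a censored observation, and likewise for TTP and DoR, when all of these are true:

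- the therapy's start day is missing;
- therapy began after the first PD, in the same calendar month;
- a later assessment falls in another month;
- the last dose was in an earlier month, or more than one day before PD;
- the imputed day is not the PD date itself.

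Each such participant is 1/151 = 0.7% of the planned events. How many there will be cannot be derived from the SAP, which gives no frequency of partial therapy dates. If, purely as an assumption, 1% to 3% of 320 participants had a day-missing start, that is about 3 to 10 people, and only those meeting every other condition would be misclassified. The effect is probably small. The reason to act is that the rule can set the wrong status on the primary endpoint and is easy to repair.

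**What to change.** Replace the PD rule in section 6.2.7 with wording such as:

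*When the partial start date has the month and year of the first documented PD used as the PFS/TTP event date (confirmed where Table 3 requires it), assign the earlier of that PD date plus one day and the last day of the month, regardless of later assessments.*

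Keep the existing instruction to take the later date when the last-dose rule also applies. In the enumeration this left no progression wrongly censored.

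The cost is one sentence and a small change to the derivation code; the event target and power are untouched. The downside is that a therapy truly started earlier in the PD month, before PD, would be dated after it. The current clause already accepts this when the last assessment is a PD in that month.
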